5.4.2 Reporting Requirements for Serious Adverse Events and Adverse Events of Special Interest

For reports of serious adverse events and adverse events of special interest, investigators should record all case details that can be gathered immediately (i.e., within 24 hours) on the paper Serious Adverse Event reporting form and transmit to ABCSG safety department via fax. In addition the serious adverse event and adverse event of special interest information will be captured in the EDC system.

Worldwide Sites: ABCSG safety department

[contact]

Relevant follow-up information should be submitted to ABCSG safety department as soon as it becomes available and/or upon request.

5.5 FOLLOW-UP OF PATIENTS AFTER ADVERSE EVENTS

5.5.1 Investigator Follow-Up

The investigator should follow each adverse event until the event has resolved to baseline grade or better, the event is assessed as stable by the investigator, the patient is lost to follow up, or the patient withdraws consent. Every effort should be made to follow all serious adverse events considered to be related to study drug or trial-related procedures until a final outcome can be reported. *With regard to the adverse event of special interest of diarrhea, it is recommended that investigators follow every adverse event of \geq Grade 1 diarrhea with weekly patient contacts (e.g., telephone calls) and follow up until resolution. Cases that do not resolve within 1–2 weeks should be aggressively managed per protocol recommendations for gastrointestinal toxicities.*

During the study period, resolution of adverse events (with dates) should be documented on the Adverse Event eCRF and in the patient's medical record to facilitate source data verification (SDV). For follow-up reports of serious adverse events and adverse events of special interest, investigators should record all follow up information immediately (i.e., within 24 hours) on the paper Serious Adverse Event reporting form and transmit to ABCSG safety department via fax. In addition the serious adverse event and adverse event of special interest follow-up information will be captured in the EDC system. If, after follow-up, return to baseline status or stabilization cannot be established, an explanation should be recorded on the Adverse Event eCRF and paper Serious Adverse Event form, if applicable.

All pregnancies reported during the study should be followed until pregnancy outcome, and they should be reported according to the instructions provided in Section 5.4.

5.5.2 Sponsor Follow-Up

For serious adverse events, adverse events of special interest, and pregnancies, the Sponsor and/or ABCSG safety department or a designee may follow up by telephone, fax, electronic mail, and/or a monitoring visit to obtain additional case details and outcome information (e.g., from hospital discharge summaries, consultant reports, autopsy reports) in order to perform an independent medical assessment of the reported case.

5.6 POST-STUDY ADVERSE EVENTS

At the time of study completion or study discontinuation, the investigator should instruct each patient to report to the investigator any subsequent adverse events that the patient's personal physician believes could be related to prior study drug treatment or study procedures.

The investigator is not required to actively monitor patients for adverse events after the end of the adverse event reporting period (30 days after the last dose of study drug). However, the Sponsor should be notified if the investigator becomes aware of any death, other serious adverse event, or adverse event of special interest occurring after the end of the adverse event reporting period, regardless of causality. The Sponsor should also be notified if the investigator becomes aware of the development of cancer or a congenital anomaly/birth defect in a subsequently conceived offspring of a female patient exposed to study drug or the female partner of a male patient exposed to study drug.

The investigator should report these events *directly to the Sponsor or its designee, either by faxing or by scanning and emailing the Serious Adverse Event/Adverse Event of Special Interest Reporting Form using the fax number or email address provided to investigators* (see "Protocol Administrative and Contact Information & List of Investigators").

5.7 EXPEDITED REPORTING TO HEALTH AUTHORITIES, INVESTIGATORS, INSTITUTIONAL REVIEW BOARDS, AND ETHICS COMMITTEES

The Sponsor will promptly evaluate all serious adverse events and adverse events of special interest against cumulative product experience to identify and expeditiously communicate possible new safety findings to investigators, IRBs, ECs, and applicable health authorities based on applicable legislation.

To determine reporting requirements for single adverse event cases, the Sponsor will assess the expectedness of these events using the following reference documents:

- GDC-0032 Investigator's Brochure
- Local prescribing information for letrozole SmPC

The Sponsor will compare the severity of each event and the cumulative event frequency reported for the study with the severity and frequency reported in the applicable reference document.

Reporting requirements will also be based on the investigator's assessment of causality and seriousness, with allowance for upgrading by the Sponsor as needed.

An iDMC will monitor the incidence of the above-listed anticipated events during the study. An aggregate report of any clinically relevant imbalances that do not favor the test product will be submitted to health authorities.

6. STATISTICAL CONSIDERATIONS AND ANALYSIS PLAN

Primary and secondary efficacy analyses will include all patients who were included in the randomization. Final analysis will be performed after last patient, last visit (LPLV) and subsequent data cleaning, with patients allocated to the treatment arm associated by randomization.

Safety analyses will include all patients who were included in the randomization and received at least one dose of study treatment, with patients allocated to the treatment arm associated with the regimen actually received.

6.1 DETERMINATION OF SAMPLE SIZE

This study is designed for testing the effect of GDC-0032 on the two co-primary endpoints in all enrolled patients and in the *PIK3CA* MT patients and plans to enroll 330 patients in total. Assuming the *PIK3CA* mutation status will not be available (unknown) for approximately 10% of the patients and the prevalence of *PIK3CA* mutant is 40%, there will be approximately 120 patients in the *PIK3CA* MT cohort.

Given that the *PIK3CA* mutation status is not a stratification factor for randomization, there might be a possible imbalance between treatment arms within the *PIK3CA* MT cohort, which may reduce the statistical power in this cohort. To ensure the study provides sufficient statistical power even when the treatment assignment is imbalanced, the sample size was calculated based on a conservative scenario by assuming that the treatment assignment imbalance in *PIK3CA* MT is 40% versus 60%. The sample size was calculated based on a chi²-test using continuity correction ([Ury and Fleiss 1980](#)).

To control an overall, two-sided, family-wise error rate under 20% *for each analysis population*, we use a two-sided significance level of 16% and 4% for the co-primary endpoints MRI ORR, and pCR, respectively.

Assuming 10% of the patients are unevaluable for the MRI ORR, approximately 300 enrolled patients and 108 patients in the *PIK3CA* MT cohort will be evaluable for analyses. This sample size allows us to detect an absolute percentage increase of 24% in MRI ORR rate in the GDC-0032 plus letrozole arm (64%) versus the letrozole-only

arm (40%; [Smith et al. 2005](#); [Ellis and Ma 2007](#)) in the *PIK3CA* MT cohort at 80% power and 16% two-sided significance level. The minimal detectable difference for ORR is approximately 15%.

Assuming that all patients are evaluable for pCR (i.e., approximately 330 enrolled patients and 120 in the *PIK3CA* MT cohort), this sample size provides 80% power to detect an absolute percentage increase of 18% in pCR in the GDC-0032 plus letrozole arm (19%) versus the letrozole-only arm (1%, [Smith et al. 2005](#); [Ellis and Ma 2007](#)) in the *PIK3CA* MT cohort at the 4% two-sided significance level. The minimal detectable difference for pCR rate is approximately 13%.

If the prevalence of the *PIK3CA* mutation is lower than assumed, if there is more substantial treatment assignment imbalance in the *PIK3CA* MT cohort than assumed, or there is an increased number of unevaluable patients for the MRI ORR, the sample size may be increased to obtain the level of power at 80%, and the enrollment may be limited to patients with *PIK3CA* MT.

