6.4.1 Primary Efficacy Endpoint

The co-primary efficacy endpoints are (1) tumor ORR, assessed by modified RECIST criteria by breast MRI (centrally assessed) and (2) the rate of pCR in breast and axilla (total pCR) after completion of study drug.

The tumor ORR will be calculated by treatment arm in all enrolled population and in *PIK3CA* MT population. Within each population, the ORR for the two treatment arms will be compared at a two-sided alpha of 16% using a Cochran Mantel-Haenszel test, stratified by tumor size and nodal status. The pCR rate will also be calculated and compared at a two-sided alpha of 4% based on the same analytical approach as ORR. The two alpha values account for a family-wise type I error rate of 20% *for each analysis*

population. Patients with early study termination and hence missing efficacy outcome will be considered as non-responders.

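### The fixed 16%/4% split is valid but discards alpha once ORR or pCR succeeds; a step-down rule with an exact or corrected pCR re-test would recover pCR power at the same 20%

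*Protocol*

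**What the plan says.** Section 6.1 gives the aim: "To control an overall, two-sided, family-wise error rate under 20"% for each analysis population (all enrolled patients, and PIK3CA-mutant patients). It allocates the error as "we use a two-sided significance level of 16% and 4% for the co-primary endpoints MRI ORR, and pCR, respectively". Section 6.4.1 turns this into the analysis rule. Within each population, "the ORR for the two treatment arms will be compared at a two-sided alpha of 16"% with a Cochran-Mantel-Haenszel (CMH) test stratified by tumor size and nodal status, and "The pCR rate will also be calculated and compared at a two-sided alpha of 4% based on the same analytical approach as ORR". It adds that the two values account for the 20%. The synopsis says the same about the levels.

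Nowhere does the protocol pass alpha from a successful endpoint to the other. pCR is judged at 4% whatever ORR shows, and ORR at 16% whatever pCR shows.

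**The concern.** This is a weighted Bonferroni split. Section 6 places the final analysis after the last patient's last visit, so both p-values are available together. In that setting a weighted Holm procedure starts at the same 16% and 4% and then tests the remaining endpoint at the full 20%. It rejects whatever the split rejects and sometimes more.

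What is at stake is pCR power. pCR holds one fifth of the alpha, and Section 3.3.4.1 itself describes pCR as unlikely under neoadjuvant hormonal therapy, citing rates of 1.4% and 0.8% in the everolimus trial. The stated 80% power needs 19% versus 1% in the mutant cohort. Power falls off for anything smaller.

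**Working it through.** **Inputs.** From Section 6.1: ORR 64% versus 40% with 108 evaluable mutant patients; pCR 19% versus 1% with 120; allocation 40:60 in the mutant cohort; chi-square test with continuity correction. From Section 6.4.1: patients with missing outcome after early termination count as non-responders. Assumptions: the 10% unevaluable for ORR all count as non-response, so ORR is 0.9 × 40% = 36% versus 0.9 × 64% = 57.6%; correlation between endpoints 0 to 0.5 (the protocol gives none); strata ignored in the exact calculations.

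**1. The stated figures reproduce.** With control share 40% (k = 1.5), d = p2 − p1 and p̄ the weighted mean rate:

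m = [z(1−α/2)·√(p̄(1−p̄)(1+1/k)) + z(0.80)·√(p1(1−p1) + p2(1−p2)/k)]² / d²

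n(control) = (m/4)·[1 + √(1 + 2(1+1/k)/(m·d))]²

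- ORR, α = 0.16: m = 35.6, n = 42.2, rounded up to 43; total 43 × 2.5 = 107.5 (stated 108).
- pCR, α = 0.04: m = 39.9, n = 48.8, rounded up to 49; total 49 × 2.5 = 122.5 (stated 120).
- Inverted for power at the stated totals: 80.8% for ORR and 79.1% for pCR.

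**2. Error rate of the step-down.** If both nulls are true, a false claim needs ORR p ≤ 0.16 or pCR p ≤ 0.04, so at most 0.16 + 0.04 = 0.20. If only one null is true, that endpoint is tested at no more than 0.20. The 20% therefore holds under any dependence, provided each test keeps its level at 20%. Simulated error under the global null is 0.194, 0.183 and 0.162 at correlations 0, 0.5 and 0.9.

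**3. Does the pCR test keep its level at 20%?** Exact binomial enumeration, two-sided, equal pCR in both arms:

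| Layout, common pCR | Uncorrected, nominal 4% | Uncorrected, nominal 20% | Corrected, nominal 20% |
|---|---|---|---|
| 165/165, 1% | 1.1% | 24.5% | 3.7% |
| 60/60, 3% (assumed) | 1.2% | 24.3% | 4.1% |

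The uncorrected test does not keep 20%. At 60/60 it would pass on 2 versus 0 events (p = 0.156), whereas the present 4% needs 5 versus 0 (4 versus 0 gives p = 0.043). The corrected test at 20% needs 4 versus 0: difference 4/60 = 0.0667, correction ½(1/60 + 1/60) = 0.0167, standard error √[(4/120)(116/120)(2/60)(120/119)] = 0.0329, z = 1.52, p = 0.13. Over common rates up to 50%, the largest size of the corrected test is 15.4% at 60/60 and 16.9% at 165/165.

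**4. Power gained with the corrected re-test, mutant cohort 60/60.** ORR power at 16% is 84.7%. Every table significant at the uncorrected 4% is also significant at the corrected 20%, so with independent endpoints:

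P(pCR) = P4 + 0.847 × (P20 − P4)

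| pCR | P4 | P20, corrected | Step-down |
|---|---|---|---|
| 8% vs 1% | 36.2% | 52.9% | 36.2 + 0.847 × 16.7 = 50.3% |
| 10% vs 1% | 54.4% | 70.0% | 54.4 + 0.847 × 15.6 = 67.6% |
| 19% vs 1% | 95.5% | 98.4% | 95.5 + 0.847 × 2.9 = 98.0% |

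**5. The same by the protocol's approximate method (40:60).** At 19% versus 1%, pCR power is 79.1% at 4% and 96.1% at 20%. With ORR power 80.8% and independence: 79.1 + 0.808 × 17.0 = 92.8%. At correlation 0.5 it is 90%. The gain is 11 to 14 points. This is the sizing approximation, not an evaluation of an exact re-test.

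**6. All enrolled patients.** At 14% versus 1%, pCR power is already about 99% under the split, so almost nothing is gained there.

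**The case against.** The strongest reply is that nothing here is wrong. The split meets its declared 20%, its powers are right, and the protocol claims no optimality. A strict level for a rare, locally read endpoint is defensible, and at the design effect the exact gain is under 3 points.

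Most of that stands. A reader might infer that the split is an error or that the power statement fails; the reproduction above shows neither. A reader might also infer that the planned CMH test could simply be re-run at 20%, giving 36% to 73% at 8% versus 1% and 54% to 84% at 10% versus 1%. Those figures are arithmetically right for the uncorrected test, but step 3 shows that it exceeds 20% when pCR is rare. About half or more of that apparent gain is bought with an error rate the plan has not declared.

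What does not stand is the idea that 4% was set as a stricter bar for pCR. Sections 6.1 and 6.4.1 present 16% and 4% only as accounting for the 20%. Section 3.3.4.1 justifies adding pCR as useful and cheap, a rise in the minimum detected difference from 12% to 13%. Nor can this be left silently to the analysis plan, which is not shown: the protocol states the levels unconditionally, so recycling would contradict its text.

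**Conclusion.** The point holds as one of efficiency. At the same 20% per population, a step-down rule with an exact or continuity-corrected pCR re-test adds about 13 to 14 points of pCR power in the mutant cohort for 8–10% versus 1%. At 19% versus 1% it adds under 3 points by exact calculation, or 11 to 14 by the protocol's sizing approximation. These figures assume ORR power of 81–85%; the exact ones also assume 60 per arm, independent endpoints and no stratification. The gain arises only when ORR succeeds and nearly vanishes in all enrolled patients once the pCR effect is large.

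There is a price. If ORR truly works and pCR does not, the ceiling on a false pCR claim rises from 4% to the declared 20%. With the corrected test at 165/165 and pCR 1% in both arms, the actual size goes from 1.1% to at most 3.7%; it is higher where the common pCR rate is higher. The 20% remains a per-population figure, and this change does nothing about error across the two populations.

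**What to change.** Amend Sections 6.1 and 6.4.1 and the synopsis, before unblinding, to say within each population:

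> *ORR is tested at 16% and pCR at 4%, two-sided, by the stratified CMH test. If pCR is significant, ORR is re-tested at 20%. If ORR is significant, pCR is re-tested at 20% using an exact (or continuity-corrected) stratified test.*

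Name one of the two pCR re-tests in advance. Require the pCR counts per arm and a confidence interval for the difference beside any pCR claim. Keep the 16%/4% sample-size statement, which becomes conservative.

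The cost is wording in three places, with no added patients, visits or procedures. If the sponsor does want 4% as a fixed bar for pCR, it should state that reason and leave the rule as it is.

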6.4 EFFICACY ANALYSES

The primary and secondary efficacy analyses will include the ITT population; that is, all randomized patients will be included in the analyses, with patients grouped according to the treatment assigned at randomization.

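### The 80% power for MRI ORR is computed on 108 evaluable mutant patients, but the planned analysis keeps all randomized patients; on that basis the plan's own formula gives about 77% if 40% and 64% are evaluable-patient rates

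*Protocol*

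**What the plan says.** Section 6.1 expects 330 enrolled patients, 10% with unknown mutation status and 40% mutant prevalence, and concludes that "there will be approximately 120 patients in the" mutant cohort. As a deliberately conservative case it assumes that treatment assignment in *PIK3CA* "MT is 40% versus 60" percent, and it uses a chi-squared sample-size formula with continuity correction. On significance levels, "we use a two-sided significance level of 16% and 4% for the co-primary endpoints MRI ORR, and pCR, respectively".

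For response by MRI it then reduces the numbers: "Assuming 10% of the patients are unevaluable for the MRI ORR, approximately 300 enrolled patients and 108 patients in the" mutant cohort are taken as evaluable. It claims that a 24-point increase, from 40% to 64%, is detectable in the "MT cohort at 80% power and 16% two-sided significance level". The synopsis repeats this.

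The analysis sections define a different comparison. Section 6.4 specifies an intention-to-treat analysis in which "all randomized patients will be included in the analyses", and the opening of Section 6 says the same. Section 6.4.1 adds: "Patients with early study termination and hence missing efficacy outcome will be considered as non-responders". The protocol defines no evaluable-only population for the primary analysis.

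**The concern.** Removing unevaluable patients and counting them as non-responders are different operations. Removal lowers the sample size and leaves the rates alone. Non-responder counting keeps the sample size and lowers both rates, and so narrows the difference between them. Section 6.1 does the first and Section 6.4.1 does the second, so the stated 80% describes an analysis that the plan does not carry out.

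The basis also matters for later decisions. Section 6.1 allows the sample size to be raised to hold power at 80% if prevalence is lower, imbalance is greater or unevaluable patients are more numerous than assumed. That clause does not cover this point, because the gap appears at exactly the assumed 10%. Any such re-sizing would start from the same evaluable-only basis.

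**Working it through.** **Inputs (Section 6.1 unless noted).** Two-sided alpha 0.16, so z = 1.405. Control rate 0.40, active rate 0.64. Mutant cohort about 120 (330 × 0.9 × 0.4 = 118.8). Unevaluable 10%, so 120 × 0.9 = 108. Split 40:60, continuity correction. All randomized patients analysed (Section 6.4); early termination with missing outcome counts as non-response (Section 6.4.1).

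**Formula.** Power = Φ{[Δ − ½(1/n₁ + 1/n₂) − z·SE₀] / SE₁}, where SE₀ uses the pooled proportion and SE₁ the two separate proportions.

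**Step 1: reproduce the plan's figure.** n = 43.2 control and 64.8 active, 0.40 versus 0.64, Δ = 0.24. Pooled proportion 0.544, SE₀ = 0.0978, SE₁ = 0.0955, correction 0.0193.

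(0.24 − 0.0193 − 1.405 × 0.0978) / 0.0955 = 0.872, so power = 80.8%.

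The stated 80% reproduces. The required total is 107.5 against the stated 108. Without the correction it would be 90, and at 1:1 with the correction 102, so the method is identified.

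**Step 2: the same formula on the planned analysis.** With 10% of each arm counted as non-responders, control is 0.9 × 0.40 = 0.36 and active is 0.9 × 0.64 = 0.576, so Δ = 0.216. n = 48 and 72, pooled proportion 0.4896, SE₀ = 0.0931, SE₁ = 0.0905, correction 0.0174.

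(0.216 − 0.0174 − 1.405 × 0.0931) / 0.0905 = 0.749, so power = 77.3%.

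With the larger arm on control it is 77.4%; with the unrounded cohort of 118.8 it is 76.9–77.0%. Exact enumeration with the corrected test at 40:60 moves from 81.6% (108 patients) to 77.2–77.4% (120 patients).

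**Step 3: dependence on the method.**

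| Comparison | Corrected, 40:60 | Corrected, 1:1 | Uncorrected, 40:60 |
|---|---|---|---|
| 108 patients, 40% vs 64% | 80.8% | 82.3% | 85.9% |
| 120 patients, 36% vs 57.6% | 77.3% | 78.9% | 82.7% |

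The loss is about 3 points in each column. A simulated four-stratum CMH test (40,000 runs; stratum sizes are an assumption, as the protocol gives none) fell from 85.2% to 81.9% without continuity correction and from 79.8% to 76.7% with it.

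**Step 4: what would give 80% on the planned analysis.** At 120 patients split 40:60, a 25-point difference among evaluable patients (40% vs 65%) becomes 0.36 vs 0.9 × 0.65 = 0.585, or 22.5 points, with power 80.2%. To keep 24 points, the formula asks for about 130 mutant patients against 120.

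**Step 5: other readings of the inputs.**
- The rates already count missing outcomes as failures: 40% vs 64% in 120 patients gives 84.6%.
- Half of the 10% counted as non-responders and half dropped: 37.9% vs 60.6% in 114 patients gives 79.0%.
- Unequal loss, purely as an illustration: 15% on GDC-0032 and 5% on placebo gives 57%; the reverse gives 91%.

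**The case against.** The strongest objection is that the 0.9 discount is itself an assumption. Section 6.1 takes its 40% from reports on the IMPACT and P024 trials, and Section 3.3.3 describes response in both on an intention-to-treat basis. If 40% already includes unassessed patients as failures, discounting it again counts them twice, and the reduction to 108 is merely cautious. This stands as a condition. Section 6.1 applies the rates directly to the 108 left after removing unevaluable patients, so they function there as evaluable-patient rates, but the protocol does not say which is meant. Under either reading, Section 6.1 does not describe the analysis in Section 6.4.

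Three further objections stand in part:
- Section 6.4.1 plans a stratified CMH test and does not mention a continuity correction. Uncorrected, power stays above 80%.
- The 40:60 split is a declared worst case. Under simple 1:1 assignment of 120 patients, a split at least that uneven has a probability of about 3.5%. Even so, the corrected formula at 1:1 gives 78.9%.
- The non-responder rule names only early termination. A scan that is unreadable in a patient who completed treatment is not expressly covered, although such a patient remains among the randomized patients to be analysed.

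A reader might infer that the trial is underpowered for response, or that its power is near 57%. The documents support neither. The first fails for an uncorrected test and under the intention-to-treat reading of the rates. The second rests on a split of missing data that appears nowhere in the protocol, and the opposite split raises power to 91%.

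**Conclusion.** The point holds in a limited form. The stated 80% belongs to an evaluable-only comparison, and the plan analyses all randomized patients. By the plan's own method the figure for the planned analysis is about 77%, roughly 3 points below the claim. This rests on three conditions: 40% and 64% are evaluable-patient rates, 10% are unevaluable in each arm, and all of them count as non-responders. It is a misstatement of the power basis that should be corrected. It is no reason to change the endpoint, test, significance level or enrolment.

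**What to change.** In Section 6.1 and the synopsis, state whether 40% and 64% are rates among evaluable patients or among all randomized patients, and give the power accordingly.

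- **If evaluable-patient rates:** about 120 mutant patients, 57.6% versus 36% with unevaluable patients counted as non-responders, about 77% power by the stated formula (about 82% for an uncorrected CMH test). Equivalently, 80% power corresponds to a detectable difference of about 25 points among evaluable patients, or 22.5 points on the intention-to-treat scale.
- **If intention-to-treat rates:** remove the reduction to 108 and state about 85% power on 120.

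The cost is a sentence in each place. No patients are added. In the first case the stated figure becomes slightly less favourable.
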